### **8.7.1 Time to recovery**

Limited data are available in the literature regarding time to recovery after surgical or conservative treatment in peroneal nerve entrapment (35, 55). Time to recovery is defined as: the time necessary to cover the minimal age- and sex-specific normal distance in meters during the six-minute walk test AND the time necessary for foot drop recovery to an MRC-score  $\geq 4$  for ankle dorsiflexion. The minimal age- and sex-specific normal 6MWD is defined as 82% of the applied reference equation for prediction of the distance covered in the six-minute walk test (59, 60). The reference value that will be used is  $6\text{MWD}_{\text{pred}}(\text{m}) = 868.8 - (\text{age}_{\text{years}} \times 2.99) - (\text{gender} \times 74.7)$ . The value for gender is 0 if the patient is male and 1 if the patient is female (60). The reference values and equation are added to the study protocol in Appendix 5.

The reference equation of Gibbons et al. is used, because this is based on the 6MWD in healthy Caucasian patients aged between 20 and 80. Troosters et al. stresses the variability in 6MWD in a healthy population and therefore proposes to consider a 6MWD smaller than 82% of the predicted 6MWD as abnormal (59). The reference equation proposed by Troosters et al. is not used, despite the inclusion of Belgian healthy subjects, due to the fact that no patients younger than 50 years old were included in this trial. However, the average difference between the predicted 6MWD derived from the study of Troosters et al. and predicted 6MWD according to Gibbons et al. was only 8.8 meters (standard deviation 73.6 meters) (60). Other publications on reference values of 6MWD in healthy subjects were discarded because of inclusion of restricted age categories (66-69) or different ethnic groups (70, 71).

### **8.7.2 Electrodiagnostics (EDX)**

Electrodiagnostic testing will be performed at baseline (screening visit, standard of care). After randomization, EDX will be repeated after 3 months and 9 months. EDX will be conducted by a trained neurologist/rehabilitation physician (see Section 6. Study Setting). EDX after randomization is not considered standard of care. The diagnosis of peroneal nerve entrapment is based on the screening EMG and falls outside the scope of the trial. However, electrophysiologists in the participating centers are advised to follow the 'guidelines' below.

In 2005, the American Association of Neuromuscular & Electrodiagnostic Medicine (AANEM) published a practice parameter for the use of EMG (electromyography) and NCS (nerve conduction studies) in evaluating patients with peroneal neuropathy (72), based on a thorough review of the literature. These recommendations however were based on Class III and IV evidence and classified as level C recommendations, reflecting the paucity of the literature on this topic (72, 73). Nevertheless, EDX was considered useful in making and/or confirming the diagnosis of peroneal neuropathy and in providing prognostic information. Following recommendations for electrodiagnostic techniques for diagnosing peroneal neuropathy were formulated:

- Peroneal motor NCS with assessment of conduction velocity through the fibular head and in the leg with recording from the anterior tibial (TA) muscle and extensor digitorum brevis muscle (EDB).
- Orthodromic and antidromic superficial peroneal sensory NCS
- At least one additional motor or sensory NCS in the same limb with normal findings (expert opinion)

The role of needle EMG in making a diagnosis remained questionable. However, experts suggest that abnormalities on needle examination outside of the distribution of the peroneal nerve should suggest alternative or additional diagnoses (6, 72).

No limits for abnormality were suggested in the literature, so following criteria were designed based on experience and previous trials in the literature (6, 10, 21, 74-76):

- Difference in motor nerve conduction velocity across the fibular head of more than 10 m/s  
AND/OR
- Presence of a motor conduction block: delta CMAP (compound motor action potential) amplitude across fibular head > 30%

Furthermore, the presence of and extent of axonal damage and mixed involvement needs to be studied, since these patients are expected to improve later and slower (1, 23).

Following data will be collected in the eCRF (a paper source document is available to the local electrophysiologist):

- Difference in conduction velocity across the fibular head (m/s)
- Motor nerve conduction velocity (proximal and distal to the fibular head)
- CMAP distal motor latency
- Superficial peroneal sensory potential
- Conduction block: drop in amplitude (%)
- EDB-CMAP (in mV) (proximal and distal to the fibular head)
- Rest EMG abnormalities
- EMG during voluntary contraction abnormalities
- Evaluation of axonal damage
- Evaluation of mixed damage

### **8.7.3 Muscle Power Assessment (Medical Research Council's scale)**

The MRC-score is a clinical assessment. A score from 0 to 5 is used to grade the power of a muscle group in relation to the maximum expected for that muscle. The score was first published in a manuscript called '*Aids to the investigation of peripheral nerve injuries*' (77) and has since been used in many clinical trials and publications. The MRC-score is a widely used tool to assess muscle strength in peripheral nerve pathology and used on a daily basis around the world to assess strength of foot dorsiflexion in patients with foot drop. Training videos for the trial investigators will be made available, so the MRC-scoring will be more rigorously applied and inter-observer variability will be reduced a strict minimum. Several modified MRC-scores are available, taking range of motion or more subtle changes in muscle strength into account (78). However, there are several disadvantages in using modified scales. There are more possible measurements and there will be more inter-observer variability. Furthermore, the MRC-score as depicted below is more representative for daily practice.

The MRC score will be noted at every visit:

- Screening visit: treating physician
- Randomization visit: treating physician\* and outcome assessor (before, during or after randomization)
- 10 days after surgery: treating physician
- 6 weeks after randomization: outcome assessor
- 3 months after randomization: outcome assessor
- 6 months after randomization: outcome assessor
- 9 months after randomization: outcome assessor
- 18 months after randomization: outcome assessor

\* before the actual randomization to avoid bias.

MRC-score will be determined for ankle dorsiflexion, hallux extension and ankle eversion. Good outcome corresponds to an MRC-score  $\geq 4$  for ankle dorsiflexion. Assessment of muscle strength using the MRC-score is considered standard of care in the follow-up of patients with foot drop.

Medical research council (MRC) muscle strength	
MRC 0	No muscle contraction
MRC 1	Muscle contraction, no movement
MRC 2	Movement, but not against gravity
MRC 3	Movement against gravity, but not against resistance
MRC 4	Movement against resistance, but not normal strength
MRC 5	Normal strength

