## 5 TRIAL DESIGN

### 5.1 Full-scale study design

The overall objective of the foot drop trial is to test the superiority of surgical release of the peroneal nerve at 10 +/- 4 weeks after symptom onset to maximal conservative treatment. The FOOTDROP trial is designed as a prospective, multicenter, randomized, parallel-design study. A double-blind design is not possible, given the fact that both the treating physician and the patient will always know the allocated treatment strategy. The clinical researcher (= outcome assessor) will be blinded for treatment.

Subjects will be randomized 1:1 to surgery or conservative treatment (simple randomization based solely on a single, constant 1:1 allocation ratio). If a patient, that signed the informed consent form (ICF), cannot be randomised because the foot drop has recovered, this will be documented in the eCRF. After randomization, the patients allocated to conservative treatment will enter a treatment period of approximately 9 months (individualised physiotherapy program). Patients allocated to the surgical arm will undergo surgery as soon as feasible after randomization (maximum within 1 week, preferably within 2 days). For all participating patients that signed the informed consent at the screening visit, an operation day will be scheduled, maximum one week after the randomization visit (due to practical scheduling reasons). At the moment of scheduling, the patient will be unaware of this date to prevent bias (and orientation of the mindset of patients toward surgery). If a patient is allocated to the conservative arm of the trial, the scheduled operation date will be cancelled, without knowledge of the patient. To facilitate signing of the informed consent form at the screening visit, patients will be informed prior to the consultation about the study (by telephone, through the patient brochure).

Patients in the surgical arm of the trial, are allowed to follow physiotherapy after surgery. The frequency and intensity are to be determined by the treating physician. All participants are allowed to use an ankle-foot orthosis. The use of electrostimulation is not advised, although not forbidden.

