### 8.4 Blinding

Blinding of trial participants and care providers is not possible because of obvious differences between both treatment groups: one group will be surgically treated whereas the other group will receive maximal conservative treatment until the primary endpoint is assessed. However, the clinical investigator in the foot drop trial (= outcome assessor) can be blinded to treatment. All participants will be asked to wear long trousers to cover a potential scar at the level of the knee. Furthermore, all patients will be asked to apply a bandage at the site of the operation (or the site of entrapment if there was no operation). Participants are not allowed to discuss their treatment with the outcome assessor. A preassessment contact between the patient and an unblinded member should be organized prior to the study assessments, to remind and instruct patients of the blinding precautionary measures.

Patients in the surgical arm of the trial will be evaluated after 10 days. A postoperative control is considered standard of care. Assessments cannot be performed by the outcome assessor at this stage, as this will cause unblinding.

Since all health care providers have access to the electronic health record, measures should be taken to prevent unblinding of the outcome assessors. Several precautions should be considered:

- Data of assessments will be documented on a separate worksheet, outside the electronic health record so that there will be no need to access the electronic health record.
- If the outcome assessor thinks the electronic health record should be accessed, the treating physician should be consulted. Since the treating physician is not blinded, he/she can access the electronic health record if deemed necessary.

To avoid errors, the outcome assessor must be aware of the identity of the patient during the assessments. Therefore, anonymization during assessment is not possible.

Blinding the outcome assessor will create the opportunity to make an objective assessment of primary and (key) secondary outcome parameters, without increasing the risk of bias.

Until the time of unblinding for final data analysis, the randomization list is kept strictly confidential. The randomization list is accessible only by the REDCap data manager to prevent further selection bias. The statistician should neither have access to randomized treatments (or randomization list) nor even to the full database until the database has been locked for analysis.

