## 8.6 Baseline data

Baseline data can be collected by the treating physician during the **screening visit** and will be recorded in the eCRF.

- EDX characteristics (see also 8.7.2.)
- Sex (male/female)
- Height in centimetres
- Age in years
- Site of entrapment (left/right/bilateral)
- Time since onset of foot drop in weeks
- MRC score for ankle dorsiflexion and ankle eversion at presentation
- Subacute onset (>2days) of foot drop
- Weight loss during last 6 months:

- Weight loss in kg
  - Current weight
  - BMI (kg/m^2)
  - Is weight loss intentional?
  - Weight loss after bariatric surgery?
  - Rapid onset?
- Postural neuropathy
  - Habitual leg crossing?
  - Prolonged squatting?
  - Frequent kneeling?
- Exercise (dynamic compression)
- Onset after childbirth?
- Previous lumbar surgery?
- Trauma
  - Sharp/blunt
  - Inversion trauma of the ankle
  - Knee dislocation
  - Other
- Iatrogenic causes of peroneal neuropathy
  - Surgery of the hip/knee/ankle
  - Other surgery (e.g. wrong positioning during thoracic surgery)
  - Recent bracing/ pneumatic compression device/ compression wrapping
  - Other
- Metabolic/systemic disease
  - Diabetes mellitus
  - Thyroid disease
  - Vitamin deficiencies e.g. B12
  - Oncological history
  - Other
- Prolonged bedrest
- Professional occupation
- Use of alcohol in units/week
- Tinel sign at the level of the fibular head
- History of neuromuscular diseases
- Professional disability
  - Currently employed/working?
  - Ability to continue working? (last day of work if the patient is unable to work)

**Baseline assessment** for the primary and secondary endpoints analyses will be collected at the **randomisation visit** by the **outcome assessor** (blinded researcher), this will reduce inter-observer variability during follow-up. The limited baseline assessments conducted by the treating physician should be conducted before the actual randomization to avoid bias. The EQ5D-5L is only to be registered if the patient did not complete the online survey or if the patient chose to not use the online system.

Baseline primary and secondary endpoint data will include:

- MRC-score for ankle dorsiflexion, hallux extension and ankle eversion
- Gait assessment:
  - o **Distance covered during the six-minute walk test (primary outcome)**
  - o Gait speed during the 10 meter walk test
  - o Ability to walk barefoot
  - o Stanmore questionnaire
  - o Need for foot-ankle-orthosis
  - o Functional ambulation categories

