#### 8.7.4 Isometric dynamometry

Recovery of ankle dorsiflexion strength is essential in patients with foot drop. The use of dynamometry allows to document ankle dorsiflexion strength in an objective manner. Dynamometry has frequently been used to assess muscle strength in patients with foot drop (79-81). Won et al. (81) used a handheld dynamometer to assess ankle dorsiflexion strength in 52 patients with peroneal neuropathy (47 traumatic peroneal neuropathies and 3 idiopathic peroneal neuropathies). During the foot drop trial, results will be obtained and reported according to the same method.

Patients are asked to lay in a supine position, with the knees extended. The test pad of the dynamometer is placed on the dorsal head of the first metatarsal bone. The patient is instructed to perform ankle dorsiflexion with maximal muscle strength. The best of three attempts is registered. Ankle dorsiflexion is measured and reported for both ankles (in Newton). The ankle dorsiflexion strength ratio, defined as the ratio of ankle dorsiflexion strength in the affected ankle over ankle dorsiflexion strength in the healthy ankle will be calculated and reported in the eCRF. Training videos for the trial investigators will be made available, so that the inter-observer variability will be reduced to a strict minimum.

Based on the experience with isometric dynamometry throughout the FOOTDROP pilot study, following instructions are proposed to collect data in the most uniform way:

1. The ankle joint is placed in neutral position (90°). Aid the patient if necessary. Register the best of three attempts. If a patient is not able to generate any dorsiflexion strength, do not apply resistance, to avoid registering passive resistance.
2. The ankle joint is placed in 'natural position'. The natural position is defined as the position of the ankle joint in the sagittal plain when the patient is neither actively dorsiflexing or plantarflexing the ankle joint. Since the natural position is depending on muscle tone in both the dorsiflexion and plantarflexion muscles, this is patient (and time) dependent. Register the best of three attempts. If a patient is not able to generate any dorsiflexion strength, do not apply resistance, to avoid registering passive resistance.

3. Register normal strength in both positions at the contralateral healthy site in order to calculate the two relevant ankle dorsiflexion strength ratios (in neutral (90°) and natural position).

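### Protocol 8.7.3 lets the outcome assessor take the baseline MRC score after randomisation, and no visible section places the other baselines, including both six-minute walks, before allocation

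*Protocol*

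**What the plan says.** Section 8.6 states that baseline assessment "for the primary and secondary endpoints analyses will be collected at the" randomisation visit, by the outcome assessor. The list that follows includes the six-minute walk distance (6MWD), marked as the primary outcome. Its only ordering rule is "The limited baseline assessments conducted by the treating physician should be conducted before the actual randomization to avoid bias".

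Section 8.7.3 lists who scores MRC at each visit. For the randomisation visit it names the treating physician, with an asterisk, and the "outcome assessor (before, during or after randomization". The asterisk leads to the footnote "before the actual randomization to avoid bias" and is attached to the physician only.

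Section 8.7.5 has the six-minute walk done twice at each visit, as the first and the last assessment, and records the better distance. It does not place either walk relative to allocation. The procedures table in 8.8 has a single randomisation column. The sections on dynamometry, Stanmore, 10-metre walk, functional ambulation, EQ-5D and WPAI speak of baseline, randomisation or the randomisation visit without an order. The flow chart is not reproduced in the available text.

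On blinding, 5.1 says that "both the treating physician and the patient will always know the allocated treatment strategy", and 8.4 that "Blinding of trial participants and care providers is not possible because of obvious differences between both treatment groups".

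**The concern.** The protocol recognises that a baseline taken after allocation can be biased, but applies the safeguard only to the physician's scores. The endpoint baselines come from the assessor. Assessor blinding keeps the assessor's judgement neutral; it does nothing for the patient's effort or self-report. Section 8.7.4 says "The patient is instructed to perform ankle dorsiflexion with maximal muscle strength", the walk asks for as much distance as the patient can cover, and the EQ-5D is self-completed. The protocol takes this kind of influence seriously elsewhere: under 5.1 an operation slot is booked for every consenting patient, but "the patient will be unaware of this date to prevent bias (and orientation of the mindset of patients toward surgery").

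Baseline 6MWD enters the primary endpoint (change to 9 months), the secondary changes at 6 weeks, 3, 6 and 18 months, and the constrained longitudinal model of 11.4.3. That model takes baseline as a response and assumes equal baseline means in the two arms. Randomisation secures this in expectation only for values that knowledge of the allocation cannot have influenced.

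For MRC itself little is at stake. Baseline MRC enters neither the primary nor the key secondary endpoint definition, and a physician's score before randomisation exists. The direct effect is confined to the strength comparisons.

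**Working it through.** **Reading the sections together.** 8.7.3 allows the assessor's MRC after randomisation. 8.7.5 makes the second walk the last assessment of the visit. If the permission is used, the second walk also falls after allocation, and the recorded best distance may come from it. The protocol does not say that this happens; it permits it.

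**The protocol's own figures.** Effect size 0.5, two-sided 5%, 90% power: the exact two-sample t-test needs 85.03, so 86 per arm = 172 (power 90.3%). 172/0.95 = 181.05, so 182 with equal arms. Both stated totals reproduce. The example minimal important difference in 8.7.5 is 0.10 × 0.82 × (868.8 − 2.99×55 − 0.42×74.7) = 55.2 m.

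**Inputs that are assumptions.** The protocol gives no SD, correlation or shift.
- SD of change: 55.2/0.5 = 110.4 m, range 80–140 m. The protocol does not itself link these two numbers.
- Baseline-to-9-month correlation rho: 0.5, range 0.3–0.7; equal SD at both visits.
- 86 analysed per arm; a shift of 10 m in one arm's baseline.

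**Formulas.**
- Single-visit SD = SD of change / √(2(1 − rho)).
- SE in the planned model = single-visit SD × √(1 − rho²) × √(2/86).
- Absolute bias = rho × shift in recorded baseline, with sign opposite to the surgery-minus-conservative baseline shift.
- Two-sided type I error = P(|Z + bias/SE| > 1.96).

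At rho 0.5: single-visit SD = 110.4/√1 = 110.4; SE = 110.4 × 0.866 × 0.1525 = 14.58 m.

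**Case A: the whole baseline 6MWD follows disclosure, 10 m shift.**

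| SD of change | rho | SE (m) | Bias (m) | Type I error |
|---|---|---|---|---|
| 110.4 | 0.3 | 13.57 | 3 | 5.56% |
| 110.4 | 0.5 | 14.58 | 5 | 6.36% |
| 110.4 | 0.7 | 15.52 | 7 | 7.36% |
| 80 | 0.5 | 10.57 | 5 | 7.60% |
| 140 | 0.5 | 18.49 | 5 | 5.84% |

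A simulation of 4,000 trials with a baseline-adjusted model at rho 0.5 agrees: 6.4% rejection and 4.7 m bias with the shift, 4.5% without.

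**Case B: only the second walk follows disclosure.** The recorded shift is E max(run 1, run 2 + g + d) − E max(run 1, run 2 + g), where d = ±10 m is the effort change and g the learning gain. Run errors are assumed independent with SD 15–35 m.
- g = 0: absolute shift 4.1–5.9 m, bias about 2–3 m, type I error 5.2–5.5% at rho 0.5.
- g = 10–20 m (8.7.5 names a learning effect but gives no size): absolute shift 5.4–8.8 m, bias 2.7–4.4 m, type I error 5.4% to about 6%.

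A second simulation (20,000 trials, run SD 25 m, d = −10, Monte Carlo error about 0.3 points) gave 5.1% with no shift, 5.1% with bias 2.1 m at g = 0, and 6.0% with bias 3.2 m at g = 20.

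**Power at 55.2 m, if the bias runs against surgery.** P(Z > 1.96 − (55.2 − bias)/14.58) = 96.6%, 95.4%, 94.8% and 93.1% for bias 0, 2.05, 2.95 and 5 m. The starting value exceeds 90% because the model adjusts for baseline.

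**The case against.** The permission covers MRC only, and MRC carries little weight. For the walk the protocol is silent, and the flow chart that might show the order is not available. The different treatment of physician and assessor has a rationale: the physician is unblinded and the assessor is not. Bias in the walk needs three things together: testing after allocation, a patient who has already been told, and effort that changes differently by arm. Section 8.3 describes a REDCap allocation documented by e-mail and does not say when the patient learns it. Every numerical input is assumed, and the resulting effect is small.

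Much of this stands as a limit on size. The protocol does not state that any walk follows allocation, and the figures are illustrations. It does not remove the point. The stated rationale protects the assessor's judgement, not the patient's effort. With surgery due within a week of randomisation, preferably within 2 days, disclosure at this visit is plausible.

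One correction to the error rate is fair. Section 11.4.3 claims superiority only if p < 0.05 and surgery improves more. With a 5 m bias and SE 14.58 m, the false-superiority rate is P(Z > 1.96 − 0.343) = 5.3% if the bias favours surgery, or P(Z > 1.96 + 0.343) = 1.1% if it runs the other way, against a nominal 2.5%. The direction is unknown, so the two-sided 6.4% should not be read as the risk of a false claim for surgery.

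The order also has a practical cost. The second walk closes the visit, so the whole battery must finish before allocation. Pilot follow-up assessments averaged 71 to 76 minutes, with a maximum of 120, and randomisation is limited to office hours. This looks manageable.

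**Conclusion.** The concern holds and is minor. Section 8.7.3 expressly allows an assessor baseline after allocation, and no visible section keeps the primary-endpoint baseline before it. Under the assumed inputs, a 10 m shift in one arm gives a bias of 3–7 m if the whole baseline is affected and about 2–4.4 m (at correlation 0.5) if only the second walk is. Two-sided type I error stays between 5.2% and 7.6%, and power at 55.2 m stays at or above 93.1% at SD 110.4 m and correlation 0.5. Whether any shift would occur, its size and its direction cannot be known from the protocol. The reason to act is that a baseline influenced by knowledge of the allocation cannot be repaired at analysis, while preventing it costs very little.

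**What to change.** In 8.7.3, replace the three-way option for the outcome assessor's score with a plain requirement that it be taken before randomisation. In 8.6, extend the existing sentence on the physician's assessments to all outcome-assessor and patient-reported baselines, naming both six-minute walks, to be completed before the REDCap randomisation is performed. Record any baseline taken later as a protocol deviation.

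The cost is two wording edits and a fixed order within one existing visit, with the full battery scheduled so that allocation can still follow in office hours. No extra visit, staff, patients or analysis is needed. The sample size (172 evaluable, 182 enrolled) and the primary model are unchanged.
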